8.9. Study medication Management

8.9.1. Accountability

The investigator or designee will maintain an accurate record of the receipt of the study medications as shipped by Castle Creek Pharmaceuticals, LLC (or designee), including the date received and the condition of the study medications. One copy of this receipt will be returned to Castle Creek Pharmaceuticals, LLC when the contents of the study medication shipment have been verified and one copy maintained in the study file. In addition, an accurate study medication disposition record will be kept, specifying the amount dispensed to each subject/caregiver and the date of dispensing. This inventory record will be available for inspection at any time. At the completion of the study, the original inventory record will be available for review by Castle Creek Pharmaceuticals, LLC upon request.

8.9.2. Return and disposition of study supplies

At the completion of the study, all unused study medication will be returned to Castle Creek Pharmaceuticals, LLC (or designee) for disposal per Castle Creek Pharmaceuticals, LLC's (or designee's) written instructions.

8.10. Other Study Supplies

Castle Creek Pharmaceuticals, LLC (or designee) will provide the following items to each investigational center prior to the initiation of subject enrollment:

- Supplies and instructions for collecting, labeling, shipping and result reporting for the clinical laboratory tests
- Urine pregnancy tests
- Supplies and instructions for blister lancing
- Equipment, supplies and training for taking standardized photographs
- Other supplies as identified by the study site.

8.11. Blinding

8.11.1. Verification of blinding

Blinding of the study medications is important for validity of this study. This study uses a double-blind design. The study medications are indistinguishable in appearance, packaging and labeling.

8.11.2. Un-blinding the study medication

Blinding is important for validity of this clinical study. However, the blind may be broken in the event of a medical emergency, in which knowledge of the study medication identity is critical to the management of the subject's course of treatment. Before breaking the blind the investigator should determine that the information is necessary (*i.e.*, that it will alter the subject's immediate course of treatment). In many cases, particularly when the emergency is clearly not study medication-related, the problem may be effectively managed by assuming that the subject is receiving an active study medication without the need for un-blinding. If deemed necessary to break the blind for a study subject, the investigator has the final decision and unilateral right to break the blind and should notify the Castle Creek Pharmaceuticals, LLC Medical Monitor as soon as possible after breaking the blind for a subject.

To identify a subject's study medication the investigator or designee must electronically contact the Medpace, Inc. IRT system to identify a subject's study medication assignment. Record the date of un-blinding, the reason for un-blinding and the initials of the investigational center staff member who performed the un-blinding on the subject's study file.

Any subject whose blind has been broken must be discharged from the study.

Instructions for use of the IRT system will be provided to each investigator prior to the initiation of subject enrollment at her/his center.

9. STUDY ASSESSMENTS

The investigator, or a designated and appropriately trained staff member, will perform the efficacy assessments according to the schedules noted below.

The same individual should perform the assessments for a given subject throughout the study. If this becomes impossible, an appropriate designee with overlapping experience with the subject and study should perform the assessments.

Similar lighting conditions and subject positioning should be used for all evaluations for a given subject.

9.1. Effectiveness Evaluations

For this study an EBS lesion is defined as a blister, or the crust and/or erosion arising from a previous blister, and the immediately surrounding intense erythema.

9.1.1. Investigator's Global Assessment (IGA)

The IGA is the investigator's (who must be a physician or Physician's Assistant/nurse practitioner in dermatology) clinical assessment of the average overall severity of all the EBS lesions, considered together, at a particular time point. The investigator should NOT refer to any other assessments, study photographs or notes to assist with these assessments.

At Visits 1-8, the investigator will assess the subject's EBS lesions using the scale below and report the one integer that best describes the average overall severity of all the EBS lesions considered together.

Investigator's Global Assessment	
Score	Definition
0	Clear: No blisters, no erosions, no crusting, no erythema and/or pigmentary changes may be present
1	Near Clear: Two or few small blisters, faint signs of erosion may be present, barely perceptible evidence of crusting, slight erythema
2	Mild: Predominantly small and some medium blisters, minimal erosions, clear crusting, definite well-defined erythema
3	Moderate: Mix of small and medium blisters, definite erosions, limited areas of crusting, marked erythema
4	Severe: Mix of medium and large blisters, marked erosions, ulceration may be present, marked and extensive crusting, intense erythema

For this evaluation, a blister is defined as a fluid filled thin-walled structure.

Blister size is defined as:

- Small: visible to $\leq 1\text{cm}^2$
- Medium: $>1\text{cm}^2$ to $\leq 2\text{cm}^2$
- Large: $>2\text{cm}^2$.

At Visit 1 (Week -6) for a subject to be enrolled, and at Visit 2 (Week 0) for the subject to be randomized, the IGA must be ≥ 3 .

At Visit 2 (Week 0) the investigator must complete the IGA prior to the first study medication application.

The IGA must be completed prior to the evaluator reviewing any study photographs.

9.1.2. Assessment Area

At Visit 1, the investigator or designee will identify an "Assessment Area" of EBS lesions to be treated. The Assessment Area is a targeted treatment area from which all IGA assessments and the primary endpoint will be made. The Assessment Area does not need to be contiguous. At Visit 1 (Week -6) for a subject to be enrolled, and at Visit 2 (Week 0) for the subject to be randomized, the Assessment Area must be $\geq 2\%$ body surface area (BSA), the IGA of the Assessment Area must be ≥ 3 , and the EBS lesions must be in one or both of the following body areas:

- Localized: plantar and/or palmar areas (plantar areas where $>25\%$ of the area has hyperkeratosis that has been present for greater than 12 weeks cannot be included as part of the Assessment Area)
- Generalized: arms, legs, torso, hands and feet (scalp, groin and areas where, in the investigator's opinion, the study medication might become occluded cannot be included as part of the Assessment Area)

In this study, the palmer method will be used to determine BSA of EBS lesion. 1% BSA is defined as the area of the subject's hand held flat, including the thumb and fingers held together. Investigational drug will be applied to the Assessment Area for the entire duration of the study 8-week treatment period.

The Assessment Area will remain fixed for the duration of the study with the notable exception at Visit 2 (see also Section 8.3). At Visit 2, the Investigator may re-designate the Assessment Area assigned at Visit 1 for purposes of inclusion provided all criteria noted above are satisfied. All IGAs and the primary endpoint will be graded from the Assessment Area.

9.1.3. Treatment Area

For purposes of this study, the Treatment Area is established after Visit 2 and is defined as all BSA where treatment is applied throughout the treatment period of the study. The treatment area may increase or decrease subsequent to Visit 2 depending on the emergence of blisters and is always inclusive of the Assessment Area. The Treatment Area is NOT the area from which the determination of BSA of EBS lesions or IGA are to be assessed; only the Assessment Area will be assigned an IGA grade and will be assessed for the BSA of EBS lesions. Additional areas of EBS lesions may be added to the Treatment Area during the Treatment Period but Treatment Area cannot be more than 30% BSA at any time. Lesions that are not being treated with study medication (i.e. occluded) are not considered as part of the treatment area. Note: A subject may never have a defined Treatment Area if the subject does not develop lesions outside of the Assessment Area during the Treatment Period.

9.1.4. Reference Lesion Surface Area (LSA)

At Visit 2 the investigator will identify one of each subject's EBS lesions, the Reference Lesion, for measurement of the LSA. The Reference Lesion should have a severity that is approximately equal to the IGA grade, however the investigator is NOT required to perform a separate IGA evaluation for the Reference Lesion.

The investigator must clearly mark the location of the Reference Lesion on the subject's body chart (*e.g.*, using landmarks and distance measurements) so the lesion can be accurately and consistently identified at subsequent visits.

At Visits 2 (Week 0), 6 (Week 8) and 8 (Week 16) the investigator will measure the length and width of the Reference Lesion using the ruler provided (or an equivalent) as follows:

- Length (*i.e.*, the length of the longest axis) to the nearest millimeter (mm)
- Width (*i.e.*, the length of the longest axis perpendicular to the length) to the nearest mm.

At Visit 2 the Lesion Dimensions must be measured prior to the first study medication application.

At Visits 6 and 8 the investigator will measure the Reference Lesion on approximately the same axes for length and width. The investigator should report 0mm for the measurements if the Reference Lesion is clear at Visits 6 or 8.

The length and width will be used to estimate the surface area of the Reference Lesion.

9.1.5. Body surface area (BSA) of the Assessment Area/Treatment Area/All EBS Lesions

All BSA measurements collected at the study site will be obtained by the investigator (who must be a physician, physician's assistant or dermatology nurse practitioner). The investigator should NOT refer to any other assessments, study photographs or notes to assist with these assessments. For this study 1% BSA is defined as the area of the subject's hand held flat, including the thumb and fingers held together.

The BSA of the Assessment Area will be collected for all lesions included within the Assessment Area using the palmar method.

The BSA of the Treatment Area will be collected for all NEW lesions that appear after Visit 2 (if new lesions exist) using the palmar method. The subject/caregiver will use the palmar method for BSA% measurement to estimate new lesions that appear after Visit 2 in between study visits (if new lesions exist) and record the information in the eDiary.

The total BSA of EBS Lesions will be collected for all lesions that are NOT being treated with study medication (e.g. lesions that exceed 30% BSA or lesions that are occluded).

9.1.6. Pruritus Intensity (for Subjects aged 8 years and older)

The Pruritus Intensity Assessment is the subject's assessment of **pruritus at its worst** experienced **over the previous 24 hours** on all EBS lesions. *The subject should NOT refer to any other assessments to assist with these assessments.*

Starting at Visit 2 (Week 0) and **continuing each day** for the duration of the subject's study participation, the subject will report his/her experience of pruritus at its worst in an **electronic diary**.

This assessment should be completed just prior to the daily study medication application using the following scale:

Pruritus Intensity											
Instructions: The following question is about itch related to your epidermolysis bullosa simplex (EBS). Please select the number that best describes your experience with itch at its worst over the past 24 hours . Please select only one answer. There is no right or wrong answer to this question.											
Rate your itch at its worst over the past 24 hours.	0	1	2	3	4	5	6	7	8	9	10
											
	No itch at all										Worst possible itch

9.1.7. Pain Intensity (for Subjects aged 8 years and older)

The Pain Intensity Assessment is the subject's assessment of **pain at its worst** experienced **over the previous 24 hours** on all EBS lesions. The subject should NOT refer to any other assessments to assist with these assessments.

Starting at Visit 2 (Week 0) and continuing each day for the duration of the subject's study participation, the subject will report the average overall intensity of pain in an electronic diary.

This assessment should be completed just prior to the daily study medication application.

Pain Intensity											
Instructions: The following question is about pain related to your epidermolysis bullosa simplex (EBS). Please select the number that best describes your experience with pain at its worst over the past 24 hours . Please select only one answer for each question. There is no right or wrong answer to this question.											
Rate your pain at its worst over the past 24 hours.	0	1	2	3	4	5	6	7	8	9	10
											
	No pain at all										Worst possible pain

9.1.8. Mobility Assessment

The Mobility Assessment is the subject/caregiver's assessment of the subject's degree of mobility over the previous 24 hours. The subject/caregiver should NOT refer to any other assessments to assist with these assessments. The same individual, subject or caregiver, should perform all Mobility Assessments for a given subject for the duration of the study. Note that the assessment of pain and pruritus must be done by the subject.

Starting at Visit 2 (Week 0) and continuing each day for the duration of the subject's study participation, the subject/caregiver will report the subject's degree of mobility by answering a series of age-appropriate questions in the eDiary. This assessment should be completed at approximately the same time each day, just prior to the study medication application, using the following scale:

Score	Definition
1	Uses wheelchair (May stand for transfers, may do some stepping supported by another person or using a walker/ frame)
2	Uses walker or frame: Without help from another person
3	Uses crutches: without help from another person
4	Uses sticks (e.g. , canes) (one or two): Without help from another person
5	Independent on level surfaces: Does not use walking aids or need help from another person (if uses furniture, walls, fences, shop fronts for support use 4 description). Requires rails for stairs
6	Independent on all surfaces: Does not use any walking aids or need any help from another person when walking over all surfaces including uneven ground, curbs, etc. and in a crowded environment
7	Crawling: Child crawls for mobility at home
8	Does not apply: For example, child does not complete the distance

This scale is assessed for 3 distances: 5 meters (yards); 50 meters (yards); 500 meters (yards).

9.2. Safety Evaluations

In addition to reporting adverse events throughout the study the investigator, a designated and appropriately trained staff member or the subject/caregiver, will perform the following safety assessments according to the schedules noted below.

9.2.1. Demographics/Medical History

At Visit 1 (Week -6), the investigator or designee will interview each subject/caregiver to obtain demographic information including date of birth, sex at birth, race and ethnicity.

Medical history information will be recorded including all medical conditions and disease states that, at Visit 1 (Week -6):

- Are ongoing
- Require concomitant therapy
- Are, in the opinion of the investigator, relevant to the subject's study participation.

9.2.2. Vital Signs

At Visits 1-8 a qualified staff member will measure each subject's vital signs. At Visit 1 (Week -6) these measurements will be part of the physical examination. The following items will be measured:

- Body temperature
- Pulse rate
- Respiration rate

- Blood pressure (systolic and diastolic) after the subject sits quietly for at least 5 minutes
- Height (at Visit 1, 6 and 8)
- Weight (at Visit 1, 6 and 8).

Abnormal vital signs must be defined as clinically relevant (CR) or not clinically relevant (NCR) on the eCRFs.

9.2.3. Physical Examination

At Visit 1 (Week -6) and Visit 6 (Week 8) the investigator or designee will perform a complete physical examination that will include, at a minimum, evaluation of the following body systems and organs:

- Skin (excluding EBS lesions)
- Cardiovascular system
- Respiratory system
- Head, eyes, ears, nose and throat
- Lymph nodes
- Gastrointestinal/Hepatobiliary (specifically assess for the presence of hepatomegaly and splenomegaly)
- Vital signs.

9.2.4. Clinical laboratory sampling

At Visits 1, 2, 4, 6 and 8 a qualified staff member will collect blood and urine samples for clinical laboratory analysis. Topical anesthetics may be used during the blood sample collection. If used the topical anesthetics should be reported as a concomitant therapy. Non-fasting blood samples will be collected at all Visits. At Visit 2 (Week 0) the samples must be collected prior to the first study medication application. The following tests will be performed:

Chemistry Panel

Albumin
Alkaline phosphatase (ALP)
Alanine aminotransferase (ALT)
Amylase
Aspartate aminotransferase (AST)
Blood urea nitrogen (BUN)
Bicarbonate
Chloride
Creatinine
Gamma-GT
Glucose

Complete Blood Count

Hematocrit
Hemoglobin
Platelet count
Red blood cell morphology
Red blood cell count
White blood cell count
White blood cell differential
% and absolute:
Basophils
Eosinophils
Lymphocytes

HbA1c	Monocytes
Lactate dehydrogenase (LDH)	Neutrophils
Lipase	
Potassium	
Sodium	Complete Urinalysis
Total bilirubin	
Total protein	
Uric acid	

The results of the clinical laboratory tests will be reported on the laboratory's standard reports. The investigator must review all laboratory reports in a timely manner and note NCR or CR to define the clinical relevance of any result that is outside the normal range for the laboratory. The investigator must date and initial every laboratory report.

The investigator must review the Visit 1 (Week -6) laboratory results for all the measured analytes for each subject prior to Visit 2 (Week 0). The subject must not be randomized at Visit 2 (Week 0) if any of the Visit 1 (Week -6) results are outside normal range for the laboratory AND, in the opinion of the investigator, CR.

The investigator must report all laboratory results that are BOTH outside the normal range for the laboratory AND, in the opinion of the investigator, CR as medical history if found prior to the first study medication treatment or as an AE if found after the first study medication treatment begins.

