8.2.2. Visit 2 (Week 0/Day 1)

This visit must occur within 42 days after Visit 1.

Subsequent study visit dates must be scheduled based on the date of Visit 2.

This visit may not occur until the investigator confirms all items necessary to determine a subject's eligibility for randomization are available.

At this visit, the investigator or designee will perform the following procedures PRIOR TO RANDOMIZATION:

1. Query the subject/caregiver about any changes in the subject's concomitant therapies since the previous visit and report changes on the appropriate form
2. Confirm the subject/caregiver continues to comply with all study restrictions and that the subject is eligible to continue in the study
3. Perform a urine pregnancy test for WOCBP; results must be negative for the subject to be randomized
4. Measure vital signs
5. Perform the IGA evaluation, IGA grade must be ≥ 3 in the Assessment Area
6. Confirm subject is eligible for randomization
7. Screen fail the study subjects who are not eligible for randomization. Note: subjects may be re-screened if, at a later date, the subject meets eligibility requirements. All protocol required procedures must be repeated (with the exception of genetic testing)
8. Perform Baseline ECG

For subjects who are eligible for randomization the investigator or designee will perform the following procedures:

1. Take standardized color photographs prior to the first study medication application
2. Determine Total BSA of the Assessment Area and of all EBS lesions using the palmar method
3. Identify the Reference Lesion and measure the Lesions Surface Area (LSA)
4. Collect blood & urine samples for clinical laboratory tests prior to the first study medication application
5. Register eligible subjects in the eDiary system in the IRT
6. Randomize eligible subjects
7. Weigh the study medication tube and dispense the tube to the subject
8. Instruct the subject/caregiver on the study medication application technique
9. Observe the first study medication application
10. Weigh the study medication tube after the first study medication application and then return the tube to the subject
11. Monitor the subject for at least 20 minutes after the application to detect any adverse events

12. Dispense a blister lancing kit and instructions to the subject/caregiver if needed
13. Review the study instructions, including eDiary, use of body charts and approved bland, non-medicated, emollient/moisturizer use, with the subject/caregiver

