Any medical condition already present at Visit 1 (Week -6) should not be reported as an adverse event unless the medical condition or signs or symptoms present at Visit 1 (Week -6) worsens in severity or seriousness at any time during the study. In this case, it should be reported as an adverse event.

Clinically significant abnormal laboratory or other examination (*e.g.*, electrocardiogram) findings that are detected during the study or are present at Visit 1 (Week -6) and worsen during the study to the point where the investigator defines it as clinically significant

should be reported as adverse events. The Investigator will exercise his or her medical and scientific judgment in deciding whether an abnormal laboratory finding or other abnormal assessment is clinically significant. Clinically significant abnormal laboratory values occurring during the clinical study will be followed until repeat tests return to normal, stabilize, or are no longer clinically significant. Any abnormal test that is determined to be an error does not require reporting as an adverse event.

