3.2. Safety Variables

3.2.1. Adverse Events

Adverse events (AEs), which include clinical laboratory test variables, will be monitored and documented from the time of the first study medication application until the subject's study participation is complete (Week 16). Beginning with the start of the first study medication

application, investigators should make an assessment for adverse events at each visit and record the event on the appropriate AE electronic Case Report Form (eCRF). All AEs that occur after the first study medication application and up to 30 days after the subject's last study medication application will be considered treatment-emergent adverse events (TEAEs).

In concert with system-organ classification (SOC) defined by MedDRA the following AEs will be categorized as AEs of special interest (AESIs) in this study:

- All gastrointestinal (GI) disorders defined by MedDRA SOC
- Hepatic Injury
- Pancreatitis
- Urticaria/angioedema
- Epidermal necrolysis
- Drug reaction with eosinophilia and systemic symptoms (DRESS)
- Purpura/cutaneous vasculitis
- Jaundice

Each AE shall be evaluated for the severity, seriousness, duration, resolution, action taken and its relationship with the study medication.

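### Protocol 9.2.4 classes laboratory abnormalities by when they are found, so a clinically relevant pre-dose Visit 2 result that returns after dosing must be reported as an adverse event

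*Protocol*

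**What the plan says.** Protocol 9.2.4 requires the investigator to report every laboratory result that is both out of range and clinically relevant: as medical history if it is found before the first treatment, "or as an AE if found after the first study medication treatment begins".

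The same section fixes the timing of the baseline sample: "At Visit 2 (Week 0) the samples must be collected prior to the first study medication application". Protocol 8.2.2 repeats this ("Collect blood & urine samples for clinical laboratory tests prior to the first study medication application") and places sampling, randomisation and the first dose ("Observe the first study medication application") at one visit. The only results that 9.2.4 requires to be reviewed before randomisation are those from Visit 1.

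Protocol 10.1 starts AE monitoring at the first application. On conditions that already exist it says: "Any medical condition already present at Visit 1 (Week -6) should not be reported as an adverse event", unless they worsen.

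SAP 3.2.1 defines treatment-emergent events by occurrence: "All AEs that occur after the first study medication application" and up to 30 days after the last one. SAP 6.3 takes the last measurement before the first application as baseline.

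**The concern.** An AE table should separate what was there before treatment from what arose after it. A rule based on discovery does not do that for a sample taken just before the first dose. The same Visit 2 value can be the laboratory baseline and also a reported AE, so a subject can have a laboratory AE with no change from baseline behind it.

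The panel includes liver enzymes, bilirubin, amylase and lipase, so the misfiled results could be of a kind that gets attention in the safety review. With about 40 subjects per arm, a few such entries would be visible in the AE listings. What is at stake is the cleanliness of the laboratory AE counts. No efficacy endpoint uses these data.

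**Working it through.** The plan states no figure to reproduce. The check is a comparison of texts, followed by an illustration of size.

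**Sequence at Visit 2.** In the second list of Protocol 8.2.2, the laboratory sample is step 4, randomisation step 6 and the observed first application step 9. No step between them calls for Visit 2 results. Protocol 8.10 lists among the site supplies "Supplies and instructions for collecting, labeling, shipping and result reporting for the clinical laboratory tests". Shipping makes a result after the visit likely, but no turnaround time is given.

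**Which results are affected.** Under 9.2.4 a clinically relevant Visit 1 abnormality bars randomisation. A clinically relevant Visit 2 result in a randomised subject is therefore new, or has become clinically relevant, since Visit 1, a gap of up to 42 days.

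**What each rule does with such a result, if it is learned after dosing:**

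| Text | Keyed to | Outcome |
|---|---|---|
| Protocol 9.2.4 | when the result is found | must be reported as an AE |
| Protocol 10.1, AE collection period | first application | the abnormality predates the period |
| Protocol 10.1, exemption for existing conditions | Visit 1 | not exempt, because it arose after Visit 1 |
| Protocol 10.1, laboratory findings | detection during the study, or presence at Visit 1 with worsening | AE if clinically significant |
| SAP 3.2.1 | occurrence after first application | not treatment-emergent if dated by its sample and ordered before the dose |
| SAP 6.3 | last value before first application | laboratory baseline |

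The 9.2.4 rule therefore conflicts with the AE collection period in 10.1, and nothing else in 10.1 removes the conflict.

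**Treatment-emergent status.** SAP 5.2 counts study days by calendar date, with the day of first treatment as Day 1. A pre-dose sample and the first dose share that date, and the SAP has no rule for ordering them. Nor does it say whether a laboratory AE is dated by sample or by report. Entered under the report date, the event falls after the first application. Entered under the sample date, it falls on Day 1 and its status is undefined.

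**Size (assumed rates).** Let p be the proportion of 80 randomised subjects with a clinically relevant Visit 2 result. The expected number of misfiled AEs is at most 80 × p, reached if every such result returns after dosing. With 40 per arm, X1 and X2 independent Binomial(40, p), and every such result misfiled:

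| p | 80 × p | P(arms differ by 2 or more subjects) |
|---|---|---|
| 1% | 0.8 | 9% |
| 2% | 1.6 | 21% |
| 5% | 4.0 | 43% |

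The expected difference between arms is 40p − 40p = 0, because the sample precedes treatment.

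**The case against.** The strongest reply is that the analysis text already protects the tables. SAP 3.2.1 counts events that occur after the first application. Protocol 11.2.4 and SAP section 8 speak of new or worsening events, the former explicitly after dosing. An abnormality in a pre-dose sample is none of these. The causality factors in Protocol 10.4.2 also expect the event to follow drug administration. This largely stands. A reader might infer that every clinically relevant Visit 2 result becomes a treatment-emergent, possibly drug-related event, and the documents do not support that. With no turnaround time given, a result known before application would be medical history under the same sentence of 9.2.4. Beyond AE reporting, status depends on the date entered.

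The collection period in 10.1 could also be read as overriding 9.2.4. But 9.2.4 is the more specific instruction and is mandatory, so a site following it would file the AE.

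A reader might further infer that early reporting of special-interest events is a by-product of this rule. It is not: Protocol 10.5.1.1 deliberately has SAEs and AESIs reported from informed consent, whatever their cause.

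Finally, the effect is noise, not bias, and the rates are assumed. Both statements are correct, and they limit the point to a minor one.

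**Conclusion.** The point holds in a limited form. As written, 9.2.4 requires an AE report for any clinically relevant Visit 2 result that is not known before dosing, although the sample is pre-dose and normally serves as baseline. This conflicts with the start of AE collection in 10.1, and the Visit 1 exemption there does not cure it. The reporting consequence follows from the text. The tabulation consequence is open, because the SAP has no dating rule for laboratory AEs and no rule for Day 1.

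On an assumed 1% to 5% of 80 subjects, at most about 0.8 to 4 AEs are misfiled, with no expected imbalance between arms and no effect on efficacy. These figures are upper limits for their assumed rates, since they take every such result to return after dosing. Severity is minor; the case for acting is that the rule is wrong as written and easy to correct.

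**What to change.** - **Protocol 9.2.4:** replace the test of when a result is found by the time of sample collection relative to the first application. A clinically relevant result from a pre-dose sample is medical history, whenever it is reported, and becomes an AE only if a post-dose result is worse.
- **Protocol 10.1:** move the anchor for existing conditions from Visit 1 to the first application, and align the adjoining sentence on laboratory findings.
- **SAP 3.2.1:** state that abnormalities from pre-dose samples are not treatment-emergent. This also settles Day 1 laboratory events.
- **Protocol 10.5.1.1:** leave unchanged, and say in 9.2.4 that the new rule does not affect reporting of SAEs and AESIs from informed consent.

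The cost is a few sentences. Slightly fewer AEs will be reported, with each displaced finding kept in medical history. The order of sample and first dose must be available. Protocol 14.1 mentions a record of sample collection but no times, so the case report form should be checked for this.
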